## Appendix 3: Sample Size Estimation and Re-estimation

### **Initial Sample Size Justification (Initial Protocol)**

*In clinical practice, the use of balanced intravenous fluids instead of chloride-rich fluids is an intervention with no increased cost and both types of fluids are equally available to the practitioner. Therefore any difference between treatment groups is clinically meaningful in regards to the MAKE30 primary endpoint. In previous studies using the MAKE30 composite endpoint in critically ill patients, the development of this endpoint occurred at a rate of 22%. SMART-MED is anticipated to enroll between 3,000 and 3,600 patients over the one year study period. Barring logistical difficulties, SMART-SURG is anticipated to enroll between 5,000 and 6,500 patients over the one year study period. Enrollment of 8,000 patients in the SMART study overall would allow detection of a difference of 2.6% in the incidence of the primary endpoint with 80% power using a type I error of 0.05.*

### **Revised Sample Size Justification (Protocol Revision 5/10/16)**

The initial protocol called for a study duration of 12 months in 5 units (60 unit-months) based on an anticipated MAKE30 event rate of 22.0%. This event rate was based on prior observational data[24], but was not specific to the study institution.

We have subsequently conducted a pilot trial in the medical ICU and examined a small amount of observational data regarding the incidence of MAKE30 in the non-medical ICUs. These data suggest (1) variation in the rate of MAKE30 between ICUs and (2) an overall rate of MAKE30 in the range of 15-17%, lower than anticipated in our initial power calculation. In order to retain adequate power to detect a relative risk reduction in the initially specified range, we plan to increase the duration of the study to include a total of 82 unit-months over a calendar period of two years.

**Based on data from the year prior we anticipate the total enrollment in SMART to be around 14,000 and the overall rate of MAKE30 to be around 15%, resulting in a detectable absolute risk reduction of 1.9% or relative risk reduction of 12%. The largest prior trial of saline versus balanced crystalloids reported a point estimate for the relative risk reduction in favor of balanced crystalloids of 12%[13].**

## **Appendix 4: Interim Analyses**

### ***Interim Analysis (Initial Protocol)***

*Enrollment will occur over an expected one year period in which all Vanderbilt ICUs are randomly assigned to one month blocks of alternating balanced fluids only or 0.9% saline only. Blocks will be only one month in length to minimize the effect of seasonal variability.*

*Thirty days after the conclusion of the sixth month of the study, the DSMB will review one interim analysis to determine if further study is warranted. The stopping boundary for efficacy will be met if (1) the difference in the incidence of the primary outcome (MAKE30) between groups is greater than or equal to 2.6% with a p value less than 0.001 AND (2) the p value is less than 0.001 for either death or new renal replacement therapy. As even small differences between groups would be clinically meaningful and given the importance to determine with as much certainty as possible whether balanced fluids are superior to chloride-rich fluids, there will not be a futility stopping boundary.*

### **Interim Analyses (Protocol Revision 5/10/16)**

With the initial trial duration scheduled for 12 months in 5 ICUs (60 ICU-months), we planned for a single interim analysis by the DSMB 6 months after trial initiation. As part of the amendment to increase the duration of the study to 82 ICU-months over almost two calendar years, the DSMB will conduct a second interim analysis midway between the initial interim analysis and the revised study stop date. This second interim analysis will include all patients enrolled through July 31st 2016 and will use the same stopping criteria as used the first interim analysis. Specifically, the stopping boundary for efficacy will be met if (1) the difference in the incidence of the primary outcome (MAKE30) between groups is greater than or equal to 2.6% with a p value less than 0.001 AND (2) the p value is less than 0.001 for either death or new renal replacement therapy. As even small differences between groups would be clinically meaningful and given the importance to determine with as much certainty as possible whether balanced fluids are superior to chloride-rich fluids, there will not be a futility stopping boundary.

## Appendix 5: Handling of Missing Baseline Serum Creatinine Values

For patients without a measured serum creatinine between 12 months prior to hospital admission and enrollment, baseline creatinine value for the primary analysis will be estimated using a previously-described three-variable formula [creatinine = 0.74 – 0.2 (if female) + 0.08 (if African American) + 0.003 × age (in years)][25]. Multiple sensitivity analyses will employ alternative approaches to estimating missing baseline creatinine values:

- 1) A ‘complete cases’ analysis will be performed in which patients without a measured creatinine value between 12 months prior to hospital admission and enrollment will be excluded.
- 2) Missing baseline serum creatinine values will be imputed by multivariable single imputation using the R function `aregImpute` in `Hmisc` package with 5 imputations. The imputation model will include age, gender, race, group assignment, source of admission, primary diagnosis, receipt of mechanical ventilation, vasopressor receipt, prior hemodialysis, total fluids received in 30 days, UHC expected mortality, overall mortality, new RRT received, minimum creatinine value, maximum creatinine value, and final study creatinine value. Continuous variables will be transformed via cubic splines with 3 to 5 knots.
- 3) Simple imputation will be performed in which first serum creatinine value after enrollment is used as the baseline creatinine.
- 4) Simple imputation will be performed in which the highest serum creatinine value between enrollment and 30 days is used as the baseline creatinine.
- 5) Simple imputation will be performed in which the lowest serum creatinine value between enrollment and 30 days is used as the baseline creatinine.

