### **Handling of Missing Data**

Of the components of the MAKE30 primary outcome, data regarding in-hospital mortality and receipt of new renal replacement therapy are not anticipated to be missing for any patients. In contrast, the persistent renal dysfunction component of MAKE30 may suffer from missing data for serum creatinine value at baseline or between enrollment and hospital discharge. In a pilot study of 974 patients in the same hospital, 31 patients (3.2%) had no measured serum creatinine between enrollment and hospital discharge. Of these 31 patients, 6 (19.4%) died within hours of ICU admission

Principal Investigators: [name], [name]

Version Date: 6/15/17

Study Title: Isotonic Solutions and Major Adverse Renal Events Trial (SMART)

Institution/Hospital: Vanderbilt University Medical Center

and qualified for the MAKE30 outcome via the in-hospital mortality criteria. The remaining 25 (80.6%) were low acuity ICU patients with a normal creatinine value measured in the 24 hours prior to ICU admission who were discharged from the hospital within 48 hours without another serum creatinine measurement. Of these, 24 had a subsequent outpatient serum creatinine value measured in the next 90 days, all of which were in the normal range. Thus, patients without a serum creatinine measurement between enrollment and hospital discharge, who do not experience in-hospital mortality or new RRT, will be classified as having not experienced the MAKE30 outcome.

With regard to missing data for baseline serum creatinine, in the same pilot study 595 of 974 patients (61.0%) had a measured serum creatinine value between 12 months and 24 hours prior to hospital admission. Of those without such a measurement, 259 of 379 (68.3%) had a value measured between 24 hours prior to hospital admission and study enrollment. Only 120 of 974 patients (12.3%) did not have an available serum creatinine value prior to enrollment. For the main analysis, patients without a measured serum creatinine value between 12 months prior to hospital admission and enrollment will have a baseline creatinine value estimated using a previously-described three-variable formula. Multiple alternative approaches to missing baseline creatinine data will be explored in sensitivity analyses including use of complete cases, multivariable single imputation, and use of the first creatinine after enrollment or the highest or lowest creatinine during the study.

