### **Handling of Missing Data**

Of the components of the MAKE30 primary outcome, data regarding in-hospital mortality and receipt of new renal replacement therapy are not anticipated to be missing for any patients[14,22]. In contrast, the persistent renal dysfunction component of MAKE30 may suffer from missing data for serum creatinine value at baseline or between enrollment and hospital discharge. In a pilot study of 974 patients in the same hospital, 31 patients (3.2%) had no measured serum creatinine between enrollment and hospital discharge[14]. Of these 31 patients, 6 (19.4%) died within hours of ICU admission and qualified for the MAKE30 outcome via the in-hospital mortality criteria. The remaining 25 (80.6%) were low acuity ICU patients with a normal creatinine value measured in the 24 hours prior to ICU admission who were discharged from the hospital within 48 hours without another serum creatinine measurement. Of these, 24 had a subsequent outpatient serum creatinine value measured in the next 90 days, all of which were in the normal range. Thus, patients without a serum creatinine measurement between enrollment and hospital discharge, who do not experience in-hospital mortality or new RRT, will be classified as having not experienced the MAKE30 outcome.

With regard to missing data for baseline serum creatinine, in the same pilot study 595 of 974 patients (61.0%) had a measured serum creatinine value between 12 months and 24 hours prior to hospital admission[14]. Of those without such a measurement, 259 of 379 (68.3%) had a value measured between 24 hours prior to hospital admission and study enrollment. Only 120 of 974 patients (12.3%) did not have an available serum creatinine value prior to enrollment. For the main analysis, patients without a measured serum creatinine value between 12 months prior to hospital

admission and enrollment will have a baseline creatinine value estimated using a previously-described three-variable formula[29]. Multiple alternative approaches to missing baseline creatinine data will be explored in sensitivity analyses including use of complete cases, multivariable single imputation, and use of the first creatinine after enrollment or the highest or lowest creatinine during the study (see Appendix 5).

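### One sensitivity analysis for missing baseline creatinine is specified both as single imputation and as five imputations, with no combining rule; the numerical effect is small and the primary analysis is not touched

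*Combined protocol and SAP*

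**What the plan says.** For the main result, Appendix 5 of the SAP fills a missing baseline deterministically: "baseline creatinine value for the primary analysis will be estimated using a previously-described three-variable formula". It then adds a set of checks: "Multiple sensitivity analyses will employ alternative approaches to estimating missing baseline creatinine values". There are five. Item 1 drops the patients concerned. Items 3 to 5 substitute the first, highest or lowest creatinine after enrollment. Item 2 is the only one that models the missing value: "Missing baseline serum creatinine values will be imputed by multivariable single imputation using the R function" aregImpute, in the Hmisc "package with 5 imputations".

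The SAP section Handling of Missing Data lists the same checks as "including use of complete cases, multivariable single imputation, and use of the first creatinine after enrollment", with no number of imputations. Section 12.0 of the final protocol (version 6/15/17) and the published protocol paper also name single imputation without a number. No text supplied says whether the five imputations are analysed separately and pooled, averaged, or reduced to one.

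On the amount of missing data, the SAP reports from the pilot: "Only 120 of 974 patients (12.3%) did not have an available serum creatinine value prior to enrollment".

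**The concern.** Single imputation produces one completed data set and treats each filled value as known. Five imputations produce five completed data sets and need a rule for combining them. The sentence asks for both and supplies no rule, so three different analyses fit the text: pool five fits, average five draws per patient, or use one draw.

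They need not agree. Persistent renal dysfunction is a cut-off, final creatinine at or above 200% of baseline. Averaging the draws narrows the spread of imputed baselines and can classify patients differently from separate draws, so the estimate may move as well as its standard error. Averaging and single-draw analysis both leave out between-imputation variance.

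What is at stake is the one model-based check on the baseline assumption. The SAP's closing section makes any analysis outside the document post hoc, so the prose should show which version was pre-specified. At present it does not.

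**Working it through.** **The plan's own figure.** Of 974 pilot patients, 595 had a creatinine between 12 months and 24 hours before hospital admission, leaving 974 − 595 = 379. Of these, 259 had a later value before enrollment, leaving 379 − 259 = 120. Then 120/974 = 12.3%, as stated. At the planned 14,000 patients this share would be 14,000 × 120/974 ≈ 1,725.

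**Formula.** Let W be the within-imputation variance, B the between-imputation variance and f the fraction of missing information, so that B/W = f/(1 − f). Rubin's total variance for m imputations is T = W + (1 + 1/m)B. The naive standard error from one completed data set is √W.

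**High case, f = 0.123.** This supposes that the whole outcome is unknown for every patient without a baseline and that nothing else predicts it.

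- B/W = 0.1232/0.8768 = 0.1405.
- Five imputations pooled: √(1 + 1.2 × 0.1405) = 1.081. The naive standard error is 1 − 1/1.081 = 7.5% below the pooled one.
- One draw, true variability: √(1 + 2 × 0.1405) = 1.132. The naive standard error is 11.6% below the truth, and a nominal two-sided 0.05 test of this sensitivity analysis would run at about 0.083.

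**Lower values of f**

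| f | Below pooled SE (m = 5) | Below true one-draw SE | Actual level of a 0.05 test |
|---|---|---|---|
| 0.01 | 0.6% | 1.0% | 0.052 |
| 0.05 | 3.0% | 4.9% | 0.062 |
| 0.123 | 7.5% | 11.6% | 0.083 |

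**Allowing for the known components.** The SAP does not expect death or new RRT to be missing, so only patients without either can have an unknown status. Let s be the share of MAKE30 due to persistent dysfunction alone. The documents do not give it; 20% and 40% are assumed. With 15% MAKE30 overall and no predictors, the part of the outcome variance that depends on baseline is (1 − q)r(1 − r), where q = 0.15(1 − s) and r = 0.15s/(1 − q). It is compared with 0.15 × 0.85 = 0.1275.

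- s = 0.2: q = 0.12, r = 0.0341, variance part 0.0290, B/W = (0.0290/0.1275) × 0.1405 = 0.032. Shortfall against the pooled standard error: 1 − 1/√(1 + 1.2 × 0.032) = 1.9%.
- s = 0.4: q = 0.09, r = 0.0659, variance part 0.0560, B/W = 0.062. Shortfall: 3.5%.

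A simulation (14,000 patients, 15% MAKE30, 12.3% missing, 1,000 runs per setting) imputed dysfunction status directly within treatment group and strata of a predictor. For s of 20–40% the naive standard error of the log odds ratio was 0.047 and the pooled one 0.048 to 0.049. The shortfall was 1.9% and 3.4% with no predictor, and 1.6% and 2.8% with a useful one. Against the true one-draw standard error, the same B/W values give 1 − 1/√(1 + 2B/W), about 3% and 5.7% with no predictor.

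**The case against.** The strongest reply is that asking for five imputations is at least as consistent with ordinary multiple imputation under a wrong label. The SAP says complete R code is in an additional file. That file is not among the documents, and it may pool five fits. This stands: a loss of precision is shown only for two readings of the prose, not for the analysis as coded. The prose would still name the wrong method.

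A second reply is that the three-variable formula and items 3 to 5 also treat filled values as known, so item 2 is held to a stricter standard. That is fair as far as it goes. But each of those rules is determinate, and a reader knows what will be run. Item 2 is not.

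A third reply is that the effect is small. Patients with prior RRT cannot meet the dysfunction criterion. Patients with no creatinine after enrollment who neither die nor start RRT are non-events by rule. The imputation model also includes minimum, maximum and final creatinine, death and new RRT, all of which should reduce the missing information. This stands too, and it sets the weight of the point.

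A reader might take the repetition of the phrase in four places as evidence that single imputation was intended. The documents do not support that. The revision histories show that the protocol incorporated the published SAP and that the SAP did not change before publication, so these are copies of one text.

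**Conclusion.** The written rule for this one sensitivity analysis contradicts itself and needs correcting. If one draw or an average is analysed as observed, the standard error is too small. At f = 0.123 the shortfall is 7.5% against the five-imputation pooled value and 11.6% against the true one-draw value. It is about 1.6–3.4% against the pooled value if persistent dysfunction alone makes up 20–40% of MAKE30. That share and the strength of the imputation model are assumptions. No figure was computed for averaging.

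Three stronger readings should be resisted. A reader might infer that the trial's main result is at risk; it is not, because the primary analysis uses the formula. A reader might infer that the standard error will certainly be understated; the unseen code leaves that open. A reader might also compute 1/√(1 − 0.123) − 1 = 6.8% and call it a ceiling. That is the limit for infinitely many imputations and bounds neither case above. Nor is 12.3% a cap on missingness: protocol section 5.0 places the pilot in the medical ICU, and the trial adds four other units.

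**What to change.** In Appendix 5, item 2, name the method multiple imputation with m of at least 5. State that persistent renal dysfunction and MAKE30 are derived within each completed data set, that the primary mixed-effects model is fitted in each, and that the log odds ratios are pooled with Rubin's rules. Correct the word *single* in Appendix 5 and in the Handling of Missing Data sections of the SAP and of final protocol section 12.0. For the published protocol paper, note the correction when results are reported.

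Check the R code against the new sentence. The cost is one sentence, the matching wording changes and, if the code does not already pool, one pooling step. No new data are needed.

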## Statistical Analysis Plan Publication

The Statistical Analysis Plan described in this document represents the final Statistical Analysis Plan for the SMART trial, and supersedes any prior versions. Any analyses not contained in this document that are performed by investigators or requested by reviewers will be considered *post hoc*. This Statistical Analysis Plan was:

- Completed on December 9, 2016
- Submitted for Publication on December 12, 2016
- Accepted on March 1, 2017
- Published online on March 16, 2017

[name], [name], [name], et al. Balanced crystalloids versus saline in the intensive care unit: study protocol for a cluster-randomized, multiple-crossover trial. *Trials* 2017;18(1):129.

STUDY PROTOCOL

Open Access

## Abstract

**Background:** Saline, the intravenous fluid most commonly administered to critically ill adults, contains a high chloride content, which may be associated with acute kidney injury and death. Whether using balanced crystalloids rather than saline decreases the risk of acute kidney injury and death among critically ill adults remains unknown.

**Methods:** The Isotonic Solutions and Major Adverse Renal Events Trial (SMART) is a pragmatic, cluster-level allocation, cluster-level crossover trial being conducted between 1 June 2015 and 30 April 2017 in five intensive care units at Vanderbilt University Medical Center in Nashville, TN, USA. SMART compares saline (0.9% sodium chloride) with balanced crystalloids (clinician's choice of lactated Ringer's solution or Plasma-Lyte A®). Each intensive care unit is assigned to provide either saline or balanced crystalloids each month, with the assigned crystalloid alternating monthly over the course of the trial. All adults admitted to participating intensive care units during the study period are enrolled and followed until hospital discharge or 30 days after enrollment. The anticipated enrollment is approximately 14,000 patients. The primary outcome is Major Adverse Kidney Events within 30 days—the composite of in-hospital death, receipt of new renal replacement therapy, or persistent renal dysfunction (discharge creatinine  $\geq 200\%$  of baseline creatinine). Secondary clinical outcomes include in-hospital mortality, intensive care unit-free days, ventilator-free days, vasopressor-free days, and renal replacement therapy-free days. Secondary renal outcomes include new renal replacement therapy receipt, persistent renal dysfunction, and incidence of stage 2 or higher acute kidney injury.

**Discussion:** This ongoing pragmatic trial will provide the largest and most comprehensive comparison to date of clinical outcomes with saline versus balanced crystalloids among critically ill adults.

**Trial registration:** For logistical reasons, SMART was prospectively registered separately for the medical ICU (SMART-MED; ClinicalTrials.gov identifier: NCT02444988; registered on 11 May 2015; date of first patient enrollment: 1 June 2015) and the nonmedical ICUs (SMART-SURG; ClinicalTrials.gov identifier: NCT02547779; registered on 9 September 2015; date of first patient enrollment: 1 October 2015).

**Keywords:** Intravenous fluids, Crystalloid, Saline, Renal failure, Pragmatic trial

## Background

The administration of intravenous (IV) fluid is ubiquitous in the care of the critically ill [1]. Globally, 0.9% sodium chloride (saline) is the most common resuscitation fluid, but recent data have associated saline with hyperchloremia [2, 3], metabolic acidosis and renal vasoconstriction [4, 5], acute kidney injury (AKI) and renal replacement therapy (RRT) [6], and increased mortality [7, 8]. Although several observational studies [7, 9–11], a before-and-after trial [6], and meta-analyses [8, 12] suggested increased rates of AKI, RRT receipt, and death with saline compared with balanced crystalloids, researchers in two recent randomized pilot trials found no difference between crystalloids in any patient outcome [13, 14]. The number of patients enrolled in these pilot trials was insufficient to exclude small but potentially clinically meaningful differences in patient outcomes between saline and balanced crystalloids. Thus, the optimal choice of isotonic crystalloid for the treatment of critically ill adults remains unknown [15, 16]. To determine the impact of balanced crystalloids compared with saline on clinical outcomes among critically ill adults, a large, prospective, controlled trial is needed [13, 17].

The aim of the present trial is to compare the effect of balanced crystalloids with that of saline on the development of major adverse kidney events (the composite of death, new RRT, or persistent renal dysfunction) among intensive care unit (ICU) patients. Secondary aims are to evaluate the effect of balanced crystalloids with that of saline on laboratory values (serum chloride, serum bicarbonate, serum creatinine), organ injury (AKI, receipt of RRT), and additional clinical outcomes (ventilator-free days, ICU-free days, in-hospital mortality). We hypothesize that use of balanced crystalloids among ICU patients will reduce the incidence of major adverse kidney events.

